### **2.2 Secondary Objectives**

1. To determine the proportion of prolonged ileus (> 7 days) in each group
2. To determine the time to return of bowel function components in each group: time to first flatus, time to first bowel movement, time to tolerance of solid food
3. To determine the time to hospital discharge order written in each group
4. To measure the adverse event rate in each group
5. To perform subgroup analyses on each group: 0 vs. 1 or greater anastomoses, 0 vs. 1 or greater visceral resection, high vs. low amount of postoperative narcotic use (above or below the median total postoperative morphine equivalent dose of narcotics), epidural vs. no epidural

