### Secondary Endpoints:

1. Prolonged ileus will be measured by the proportion of patients who do not pass flatus or bowel movement greater than 7 days from the time of surgery
2. The time to return of bowel function components will be measured in hours from the time leaving the operating room until:
  - The time to first flatus
  - The time to first bowel movement
  - The time to tolerance of solid food
3. The time to hospital discharge order written will be measured in hours from the time leaving the operating room
4. Adverse events will be measured using CTCAEv3 criteria.
5. Primary and secondary endpoints will be measured in each subgroup

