### **9.6 Analyses of secondary endpoints**

Log-rank test will also be used to compare the time to return of bowel function outcome. A Cox proportional hazards model will also be considered for this endpoint, controlling for potential confounders such as age and gender. The proportion of patients with prolonged ileus will be compared between groups with a Pearson's chi square test. A logistic regression model will be used to assess the association between prolonged ileus and treatment, controlling for potential confounders. We will compare the time to discharge between groups with a two-sample t-test, and consider a linear regression to control for potential confounders, including opioid use (i.e. total morphine equivalents) +/- epidural placement, bowel resection, and other complications.

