### **9.7 Exploratory analyses**

For any prespecified subgroup analyses, we will include a binary covariate indicating subgroup membership in each of the regression frameworks described. We will also fit models with interactions between each subgroup and treatment group. Descriptive statistics (mean, standard deviation, counts, and percentages) and plots will be produced for all demographic, safety, and outcome variables. All analyses will be conducted using the latest version of R (R Foundation for Statistical Computing, Vienna, Austria. <http://www.R-project.org/>).

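### The optional discharge regression adjusts for postoperative opioid total and complications as if they were confounders, and the opioid total, which also defines a subgroup, has no stated time window.

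*Combined protocol and SAP*

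**What the plan says.** All references are to the combined protocol and SAP.

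- **Discharge (9.6).** The stated comparison is unadjusted: "We will compare the time to discharge between groups with a two-sample t-test". The analysts will then "consider a linear regression to control for potential confounders, including opioid use (i.e. total morphine equivalents) +/- epidural placement, bowel resection, and other complications".
- **Prolonged ileus (9.6).** A chi-square test is followed by a firm commitment: "A logistic regression model will be used to assess the association between prolonged ileus and treatment", with confounders that are not listed.
- **Return of bowel function (9.6).** After the log-rank test, "A Cox proportional hazards model will also be considered for this endpoint". This model is optional.
- **Subgroups.** Section 2.2, item 5, lists "high vs. low amount of postoperative narcotic use (above or below the median total postoperative morphine equivalent dose of narcotics") among the subgroups. Section 2.3 adds: "Primary and secondary endpoints will be measured in each subgroup". Section 9.7, headed as exploratory, says "we will include a binary covariate indicating subgroup membership in each of the regression frameworks described", and then "We will also fit models with interactions between each subgroup and treatment group".
- **The opioid total (5.3.2).** The unit is morphine equivalents and the figure is worked out once the patient has gone home. That says when it is computed, not what interval it covers.
- **Timing.** Patients are randomized before it is known whether CRS/HIPEC will be done (9.1). The first dose is given in preoperative holding (4.1).

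**The concern.** A confounder influences both treatment assignment and outcome. Randomization removes that link for anything that happens later. Postoperative opioid use and complications come after assignment and after the first dose, so each is a possible consequence of treatment or of slow recovery.

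The opioid total is the sharper problem because its window is open. If it accumulates until discharge, a patient who stays longer has a larger total simply by staying longer. Section 8.1 says the drug leaves central analgesia intact, so an arm difference in the total would come mainly through duration. Holding the total fixed then holds part of the outcome fixed, and the adjusted difference shrinks towards zero.

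The same total, split at its median, defines a subgroup. With a whole-stay total, the high-use half would partly be the slow-recovery half, and a subgroup contrast would be hard to interpret. An unstated window also leaves the analyst a choice after the data are in.

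**Working it through.** **1. The plan's own figure.** Section 9.2 pairs HR 1.59 with medians of 9 and 5.7 days: 9 / 1.59 = 5.66, which agrees. The plan states no figure for the discharge or prolonged-ileus models, so the rest is illustration.

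**2. Is the window stated elsewhere?** Section 5.3 concerns data collected during treatment, and 4.6 ends dosing by postoperative day 7. That could imply a day-7 limit. But bowel function sits under the same heading (5.3.3), and median GI-2 is 9 days (1.3), so the heading does not settle it.

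**3. Formula for a total to discharge.** Let Y be stay and R the daily dose, independent of arm and stay, with coefficient of variation c. Let M = R × Y be the total. The adjusted effect equals the unadjusted effect minus (within-arm slope of Y on M) × (arm difference in M). With V the pooled within-arm variance of stay, this gives

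fraction of effect removed = V / (V + c² × E[Y²]).

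**4. Inputs.** From the documents: control median GI-2 of 9 days, HR 1.59, median stay of 10 days (1.1). Assumed: discharge 1 day after GI-2; Weibull GI-2 with shape 2 to 4; log-normal daily dose with log-SD 0.2 to 0.7, so c² = exp(SD²) − 1 = 0.041 to 0.632.

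**5. Numbers in.**
- Shape 2: V = 20.43, E[Y²] = 113.35. At log-SD 0.2: 20.43 / (20.43 + 0.0408 × 113.35) = 82%. At 0.7: 20.43 / (20.43 + 0.632 × 113.35) = 22%.
- Shape 4: V = 5.64, E[Y²] = 95.20. At log-SD 0.2: 59%. At 0.7: 9%.

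**6. Other windows.** Simulation with 1,000,000 patients per setting, same assumptions. Tapered means that daily use falls to 20% after day 5.

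| Shape | Log-SD | To discharge, constant | To discharge, tapered | To day 7 | First 24 h |
|---|---|---|---|---|---|
| 2 | 0.2 | 82% | 42% | 17% | 0% |
| 2 | 0.7 | 22% | 5% | 2% | 0% |
| 3 | 0.2 | 70% | 25% | 8% | 0% |
| 3 | 0.7 | 13% | 2% | 1% | 0% |
| 4 | 0.2 | 60% | 16% | 4% | 0% |
| 4 | 0.7 | 9% | 1% | 0% | 0% |

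A second set of assumptions gives a similar picture: Weibull stay with control median 10 days and shape 1.5 to 4, HR 1.34 (the pooled discharge figure in 1.2), and c from 0.3 to 1.0. It gives 7-78% to discharge, 1-28% tapered, and 0-3% for a fixed 72-hour total.

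**7. Complications.** The same identity applies: the shift is the complication slope times the arm difference in complication rate. If the drug does not change that rate, the shift is zero. The documents give no figure for this.

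**8. Prolonged-ileus subgroup model.** Use 61 per arm (122 / 2), the 13% historical rate in 1.1, and HR 1.59 borrowed from GI-2. Expected control events: 61 × 0.13 = 7.9. On alvimopan: 0.13^1.59 = 0.039, and 61 × 0.039 = 2.4. That is about 10 in all, with an unadjusted odds ratio of 0.27. Adding the high/low indicator from a whole-stay total moves it to between 0.28 and 0.36, depending on the assumptions.

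For the interaction, take an even split unrelated to stay (30.5 patients per cell). The chance of at least one empty arm-by-subgroup cell is

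1 − (1 − 0.87^30.5)² × (1 − 0.961^30.5)² = 52%.

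At HR 1.16, 1.28 and 1.54, values that 1.2 reports for GI-3 at 12 mg, it is 12%, 21% and 47%.

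**The case against.** **The regression is optional.** It sits behind a stated t-test and may never be run. This stands and is the main reason for low priority.

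**A reader might infer that the opioid total is in the committed prolonged-ileus model.** The documents do not support that. Section 9.6 names no opioid covariate for that model. The split enters only through 9.7, in exploratory subgroup versions. Listing subgroups as a secondary objective in 2.2 does not change which model contains the split.

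**A reader might blame the open window for interactions that cannot be estimated.** A whole-stay total makes this worse by gathering cases in the high-use half. But an even split unrelated to stay already leaves an empty cell 52% of the time at HR 1.59. The main cause is about 10 expected events, which is a separate sparse-data point. The hazard ratio is also borrowed from a different endpoint.

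**A reader might quote attenuation above 90%.** The formula gives 42-92% if GI-2 is exponential, the form implied by the plan's conversion of the hazard ratio to medians. But that puts 1 − 0.5^(2/9) = 14% of control patients at GI-2 within 2 days, while 1.1 puts first flatus or bowel movement typically at day 4-5. Simulated alongside first flatus or bowel movement, it has 25-28% of controls reaching GI-2 earlier than that event, which the GI-2 definition rules out.

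**A reader might infer a distorted GI-2 subgroup hazard ratio.** Section 9.5 gives GI-2 only a log-rank test. The optional Cox model sits among the secondary endpoints and is not clearly a GI-2 model, and 2.3 names no model for the subgroups.

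**An early-window dose asks a different question from total use.** True; it is a cost of the fix.

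**Conclusion.** The point holds in limited form. Section 9.6 labels two post-randomization variables as confounders, and the opioid total has no stated interval. The direction of the opioid bias is clear if the total runs to discharge: the adjusted discharge effect shrinks. Its size is not known. The range of roughly 10-80% at constant use (about 1-45% tapered, 0-17% for a treatment-period total, about 0% for 24 hours) rests on assumed distributions of stay and daily dose, and on a daily dose unaffected by the drug. The top values need the least variable dosing. For complications, bias arises only if the drug changes their rate.

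In the exploratory prolonged-ileus subgroup model the treatment odds ratio would move little. Its interaction may have no finite estimate under any window. The primary log-rank test, the discharge t-test, the prolonged-ileus chi-square test, the sample size and the futility rule are unaffected. Low priority.

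**What to change.** - **Section 9.6:** delete total morphine equivalents and postoperative complications from the covariates. Adjust only for baseline variables and operative variables that treatment cannot affect: for example age, sex, bowel resection, and epidural if placed before or during surgery.
- **Sections 2.2 (item 5) and 5.3.2:** define the opioid subgroup by dose in one fixed early window common to all patients, for example the first 24 hours after leaving the operating room. Label it exploratory in 2.2 as well, because it is still measured after randomization and the first dose.
- **Opioid use:** report total use by arm as an outcome, with its interval stated.
- **Prolonged ileus by subgroup:** report event counts by arm and subgroup, and use a penalized (Firth) fit for any interaction. The window change alone does not cure sparse cells.

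**Cost.** A short amendment, with IRB approval before use (10.6). Section 5.3.2 describes only a total, so dose times may have to be extracted from the inpatient record. An early dose measures overall exposure less well and may overlap with the epidural subgroup, since epidural analgesia is part of the standard pathway (4.4).

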### **9.7 Exploratory analyses**

For any prespecified subgroup analyses, we will include a binary covariate indicating subgroup membership in each of the regression frameworks described. We will also fit models with interactions between each subgroup and treatment group. Descriptive statistics (mean, standard deviation, counts, and percentages) and plots will be produced for all demographic, safety, and outcome variables. All analyses will be conducted using the latest version of R (R Foundation for Statistical Computing, Vienna, Austria. <http://www.R-project.org/>).

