### **1.3 Rationale**

In an analysis of 50 consecutive CRS/HIPEC procedures performed at UCSD the median time to return of bowel function, as defined in prior phase III clinical trials with alvimopan (later of time to first bowel movement or tolerance of solid diet, GI-2), was 9 days. No studies have been published investigating the use of alvimopan after CRS/HIPEC. The current proposal is being performed to investigate the efficacy of alvimopan on the time to return of bowel function in patients undergoing CRS/HIPEC.

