## 2.3 Endpoints

### Primary Endpoint:

The time to return of upper and lower GI function (GI-2) will be measured as follows:

- Time measured in hours from the time leaving the operating room to the later of the following two events:
  - i. Time that the patient first tolerates solid food
  - ii. Time that the patient first passes a bowel movement
- If upper and lower GI function have not occurred by the time of discharge, the patient will be censored.

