**9.2 Sample Size and Accrual**

Our sample size calculation is based on detecting a difference in distributions of times until GI-2 between groups. Assuming a similar hazard ratio between the Alvimopan 12 mg and placebo groups as Xu et. al. (HR = 1.59, which approximately corresponds to an improvement in the median primary endpoint (GI-2) from 9 days to 5.7 days), a log-rank test for a difference in distributions of times until GI-2 is met will have 80% power at the one sided 0.05 significance level with a total sample size of n = 122. (Note that this does not adjust for a reduction in power due to the interim analysis.) Accounting for a 5% drop-out rate, the total enrolled sample size is 128 participants.

Approximately 60-70 CRS/HIPEC procedures are performed at UCSD annually. Accrual of 128 participants could occur over 2-3 years. Annual target accrual will be 40 participants per year.

Accrual Targets			
Ethnic Category	Sex/Gender		
	Females	Males	Total
Hispanic or Latino	8	5	13
Not Hispanic or Latino	63	52	115
Ethnic Category: Total of all subjects	71	57	128
Racial Category			
American Indian or Alaskan Native	0	0	0
Asian	8	5	13
Black or African American	2	1	3
Native Hawaiian or other Pacific Islander	1	1	2
White	60	50	110
Racial Category: Total of all subjects	71	57	128

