### **9.5 Analyses of the primary endpoint**

For our primary endpoint, we will use a log-rank test at 5% level to compare the distributions of times until recovery (GI-2) between groups.

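### Section 9.7 applies mean and SD to GI-2, a time censored at discharge, and no section commits to a primary GI-2 hazard ratio or median, although the design is stated in those terms

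*Combined protocol and SAP*

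**What the plan says.** - **Endpoint (section 2.3, Primary Endpoint).** GI-2 is a time in hours from leaving the operating room, and it is right-censored: "If upper and lower GI function have not occurred by the time of discharge, the patient will be censored".
- **Design (section 9.2).** The sample size rests on a hazard ratio of 1.59, described as an "improvement in the median primary endpoint (GI-2) from 9 days to 5.7 days". The historical benchmark in section 1.3 is also a median of 9 days.
- **Primary analysis (section 9.5).** One sentence: "we will use a log-rank test at 5% level to compare the distributions of times until recovery (GI-2) between groups". It names no estimate, confidence interval or median.
- **Cox model (section 9.6, secondary endpoints).** "Log-rank test will also be used to compare the time to return of bowel function outcome", followed by "A Cox proportional hazards model will also be considered for this endpoint, controlling for potential confounders such as age and gender".
- **Summaries (section 9.7).** "Descriptive statistics (mean, standard deviation, counts, and percentages) and plots will be produced for all demographic, safety, and outcome variables". Censored times are not set apart.

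**The concern.** There are two linked gaps.

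First, an ordinary mean or SD has no correct value to use for a patient discharged before GI-2. Either that patient is dropped, or the discharge time stands in for a recovery that has not happened. Both pull the mean down, and by different amounts in the two arms if the arms differ in how many patients are censored or how late those patients recover. Section 9.4 runs the primary efficacy analysis without imputing missing values, so an analyst could well treat a censored GI-2 as missing and drop it. Good practice cannot simply be assumed, because section 9.6 already uses a t-test and linear regression for another time outcome, time to discharge.

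Second, the trial is sized on a hazard ratio and explained by two medians, but the plan commits to a p-value only. A reader of the results will want to know how the observed effect compares with 1.59, or with 9 against 5.7 days. As written, whether to give that estimate, and with which covariates, could be settled after unblinding.

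**Working it through.** **1. The plan's own figures.** Freedman's formula with one-sided 5% and 80% power gives (1.645 + 0.842)² × (2.59/0.59)² = 6.18 × 19.27 = 119.1, so 120 events, against the stated 122. At 122 events the same formula gives 80.8% power. The median shift is 9/1.59 = 5.66 days, the stated 5.7. The design figures hold and rest on the hazard ratio. None depends on how GI-2 is summarised.

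**2. Inputs for the bias check.**
- From the documents: placebo median 9 days, hazard ratio 1.59, 1:1 allocation.
- Assumed, because the documents are silent: Weibull shape k from 1 to 3; censoring falls only on patients still unrecovered, at a time uniform between days 10 and 12; the share censored in each arm.
- Times: T = 9 × [-ln U / (h ln 2)]^(1/k), with U uniform on (0, 1), h = 1 on placebo and 1.59 on alvimopan.

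**3. Hand check at k = 1 (exponential), 10% versus 2% censored.** The true means are 9/ln 2 = 12.98 and 12.98/1.59 = 8.17 days, a difference of 4.81.
- *Censoring time counted as recovery.* Each censored patient loses, on average, one full mean of remaining time. The means become 12.98 × 0.90 = 11.68 and 8.17 × 0.98 = 8.01. The difference is 3.67, or 24% too small.
- *Censored patients dropped.* Their true times average about 10.97 + 12.98 = 23.95 days on placebo and 10.96 + 8.17 = 19.13 on alvimopan. The means become (12.98 - 0.10 × 23.95)/0.90 = 11.76 and (8.17 - 0.02 × 19.13)/0.98 = 7.95. The difference is 3.81, or 21% too small.

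**4. Range over k = 1, 1.5, 2 and 3** (1,000,000 simulated patients per arm). The table gives the error in the difference in means.

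| Censored, placebo / alvimopan | Dropped | Counted as recovery |
|---|---|---|
| 10% / 2% | -21% to -27% | -14% to -24% |
| 5% / 2% | -7% to -9% | -6% to -10% |
| 2% / 1% | -2% to -3% | -2% to -4% |
| 10% / 10% | 0 to +5% | -5% to -10% |
| 5% / 5% | 0 to +2% | -3% to -5% |

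The true difference falls from 4.8 days at k = 1 to 1.3 days at k = 3. Only k = 1 reproduces the 5.7-day alvimopan median; k = 3 gives 7.7 days.

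**5. A second censoring model.** With independent exponential censoring at the same rate in both arms and k = 1, the difference in means is understated by about 10% when 5% of all patients are censored and by about 32% at 17%. With no censoring the error is zero. Kaplan-Meier medians (9.0 and 5.7 days) and the Cox hazard ratio (1.59) were recovered at every level tried, from 0 to 34%. That is expected, because this censoring is non-informative.

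**6. Does section 9.6 fill the gap?** The Cox model is only considered, sits under secondary endpoints, and carries an open list of covariates. Its endpoint is unclear: section 2.3 uses the return-of-bowel-function wording for the separate components, while section 1.3 uses it for GI-2 itself ("later of time to first bowel movement or tolerance of solid diet, GI-2), was 9 days").

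**The case against.** **A hazard ratio may already be planned.** A reader might infer that no section provides for one at all. The documents do not support that. The Cox sentence in section 9.6 may cover GI-2. Section 9.7 adds subgroup terms to each regression described, and section 2.3 includes the primary endpoint in the subgroup work. This stands, and limits the point to the lack of a firm, primary, unadjusted GI-2 estimate.

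**Section 9.7 is a generic list.** It also names counts, percentages and plots, and the plots could be Kaplan-Meier curves. A reader might infer that a difference in means is the planned measure of benefit, or that the trial could not say whether 1.59 was reached. Neither follows: no passage plans a GI-2 mean difference, and the same data can give the hazard ratio. Still, no curve is named, and a plot does not commit anyone to a median with its interval.

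**Censoring may be rare.** Section 4.1 links discharge to GI-2, section 1.1 says most of the stay is spent awaiting bowel function, and median GI-2 is 9 days against a median stay of 10. This makes heavy censoring less likely without excluding it. Nothing in the documents supports 10% versus 2% in particular, and the milder rows of the table are just as admissible.

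**Kaplan-Meier and Cox are not immune.** If discharge before GI-2 is related to prognosis, they can be biased too. In the day 10 to 12 scenarios all censoring falls after both medians, so those scenarios do not test this. It is a reason to report censoring openly, but it does not favour a mean that ignores censoring altogether.

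**Conclusion.** The point holds as a gap in the planned reporting. The mean-and-SD rule in section 9.7 is unsuitable for GI-2 whenever patients are censored, and section 9.5 commits to a test without an estimate although the design is expressed as a hazard ratio and medians.

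The size of the bias is conditional. It runs from nil with no censoring to an understatement of about a quarter at 10% versus 2% censored, and under equal censoring it can go slightly either way. These figures rest on assumed Weibull shapes, censoring times and censoring shares. A reader might infer that the reported benefit will be biased regardless; without a censoring rate in the documents, that cannot be said. Nor is a false positive at issue: the log-rank test, sample size and power are untouched, and where censoring is heavier on placebo the error understates benefit. The missing primary estimate is a gap at any censoring rate.

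**What to change.** - **Section 9.5:** add, as the primary estimate, the unadjusted Cox hazard ratio for GI-2 with a two-sided 90% confidence interval, which matches the one-sided 5% test in section 9.2. Add Kaplan-Meier median GI-2 by arm with confidence intervals.
- **Section 9.7:** for censored time-to-event outcomes, replace mean and SD with Kaplan-Meier medians and quartiles. Keep mean and SD for uncensored continuous variables.
- **Section 9.6:** state which endpoint the Cox model covers.
- **Reporting:** give the number censored for GI-2 by arm, with reasons, so that readers can judge whether discharge censoring is informative.

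The cost is a few sentences in the analysis plan, settled before unblinding. Data collection and software stay the same.
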